### 3.3.4 Withdrawal of subjects from treatment or assessments

Subjects may discontinue trial treatment or withdraw consent to trial participation as a whole ('withdrawal of consent') with very different implications; see Sections [3.3.4.1](#) and [3.3.4.2](#) below.

If a subject is removed or withdraws from the trial prior to the first administration of trial medication, the data of this subject will not be entered in the case report form (CRF) and will not be reported in the clinical trial report (CTR). If a subject is removed or withdraws from the trial after the first administration of trial medication, this will be documented and the reason for discontinuation must be recorded in the CRF. In addition, the data will be included in the CRF and will be reported in the CTR.

At the time of discontinuation, a complete end of trial (EoT) examination will be performed, if possible, and the information will be recorded in the CRF. If the discontinuation occurs before the end of the REP (see Section [1.2.6](#)), the discontinued subject should, if possible, be questioned for AEs and concomitant therapies at or after the end of the REP in order to ensure collection of AEs and concomitant therapies throughout the REP, if not contrary to any consent withdrawal of the subject.

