|       |         | 34:00  | 18:00  |  |                   | x                                     | —                                    |           |                                   |        |                 |     |   | X  |                           | x                           |  |
|       | 3       | 48:00  | 08:00  |  |                   | x                                     | ▼                                    | x         |                                   |        | x  | x   | ■ | X  |                           | x                           |  |
|       | 4       | 72:00  | 8:00   | Breakfast (voluntary) 
Discharge from trial site | B    | x                                     |                                      | x         | x                                 | x      | x  | x   | ■ | X  |                           | x                           | ▼  |
| 5     | 4 to 14 |  |  | End of trial (EoT) examination                             | A                 |                                       |                                      |           | x                                 |        |                 |     |   | x               |                           | x                           | x   |

- Subject must be informed and written informed consent obtained prior to starting any screening procedures. Screening procedures include physical examination, check of demographics (including determination of body height and weight, smoking status and alcohol history), relevant medical history, concomitant therapy and review of inclusion/exclusion criteria.
- The time is approximate; procedures are to be performed and completed within the 3 h prior to drug administration. Allocation to treatment may be performed at any time following enrolment but must be completed prior to (first) drug administration.
- If several actions are indicated at the same time, the intake of meals will be the last.
- EoT examination includes physical examination, body weight, vital signs, ECG, safety laboratory, recording of AEs, and concomitant therapies.
- Only urine drug screening and alcohol breath test will be done at this time.
- AEs and concomitant therapies will be recorded throughout the trial, but will be specifically asked for at the times indicated in the [Flow Chart](#) above.

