- One additional blood sample for stability testing will be taken at this time (refer to Section [5.3.2.4](#)).
- qEEG not to be registered at SCR.
- Sampling times and periods may be adapted based on information obtained during the trial (e.g., due to preliminary pharmacokinetic data) including addition of samples and visits as long as the total blood volume removed does not exceed 500 mL per subject.
- Including blood sample for metabolite identification (refer to Section [5.3.2.2](#)).
- A blank urine sample (0.5 mL) is to be obtained prior to administration of trial medication. Other urine samples are to be collected over the stated post-dose intervals (◀—|—|—▶) 0-4, 4-8, 8-12, 12-24, and 24-48 h.

13. At baseline (i.e., Day -1, prior to drug administration) 3 triplicate ECGs are recorded within approximately one hour. The recordings should be separated by at least 15 minutes.
14. One additional blood sample for pharmacogenomics analyses (see Section [5.6.1](#)) will be taken either at Visit 2 or at a later visit.
15. If EoT is performed on Day 4, laboratory A instead of B will be performed.
16. Dissociative symptoms are reported as AEs and should be quantified with CADSS.
17. The EEG performed at the Screening Visit is to identify and exclude subjects with an unknown susceptibility for epileptiform abnormalities and/or seizures. Therefore, Screening EEG will include spontaneous EEG activity in resting condition as well as provocation maneuvers (intermittent photic stimulation and hyperventilation) . All EEGs will be reviewed by neurologists experienced in EEG reading.
18. CADSS questionnaire to be filled in before the performance of [REDACTED]
19. Preparation and randomisation of medication on Day -1 and allocation of treatment to subject only on Day 1.

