|        |       |          | 14:00  | 22:00  |   |                   | x                                  |           |                                    |        |                 |     |             |                             |  |
|        |       | 2        | 24:00  | 08:00  | Breakfast (voluntary)                                     | B                 | x                                  | x         | x                                  |        | x  | x   | x           | x                           |  |
|        |       |          | 36:00  | 20:00  |   |                   | x                                  |           |                                    |        |                 |     |             |                             |  |
|        |       | 3        | 48:00  | 08:00  |   |                   | x                                  | x         |                                    |        | x  | x   | x           | x                           |  |
|        |       | 4        | 72:00  | 08:00  | Breakfast (voluntary)
Discharge from trial site | B     | x                                  | x         | x                                  | x      | x  | x   | x           | x                           | ▼  |
| EoT    | 5     | 16 to 26 |  |  | End of trial (EoT) examination                | A                 |                                    |           | x                                  |        |                 |     | x           | x                           | x   |

- Subject must be informed and written informed consent obtained prior to starting any screening procedures. Screening procedures include physical examination, check of demographics (including determination of body height and weight, smoking status and alcohol history), relevant medical history, concomitant therapy and review of inclusion/exclusion criteria.
- The time is approximate; the procedure is to be performed and completed within the 3 h prior to drug administration.
- If several actions are indicated at the same time, the intake of meals will be the last.
- EoT examination includes physical examination, body weight, vital signs, ECG, safety laboratory, recording of AEs and concomitant therapies.
- Only urine drug screening and alcohol breath test will be done at this time.

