#### 3.3.4.1 Discontinuation of trial treatment

An individual subject will discontinue trial treatment if:

1. The subject wants to discontinue trial treatment, without the need to justify the decision
2. The subject has repeatedly shown to be non-compliant with important trial procedures and, in the opinion of both, the investigator and sponsor representative, is not willing or able to adhere to the trial requirements in the future
3. The subject needs to take concomitant medication that interferes with the investigational medicinal product or other trial treatment
4. The subject can no longer receive trial treatment for medical reasons (such as surgery, adverse events (AEs), or diseases)
5. An AE or clinically significant laboratory change or abnormality occurs that the investigator assesses as warranting discontinuation of treatment. This may include cases of sustained symptomatic hypotension (BP <90/50 mmHg) or hypertension (BP

- >180/100 mmHg), clinically relevant changes in ECG requiring intervention, unexplained hepatic enzyme elevations at any time during the trial, or development of suicidal ideation
6. The subject has an elevation of AST and/or ALT  $\geq 3$ -fold ULN and an elevation of total bilirubin  $\geq 2$ -fold ULN (measured in the same blood sample) and/or needs to be followed up according to the DILI checklist provided in the ISF

In addition to these criteria, the investigator may discontinue subjects at any time based on his or her clinical judgment.

Even if the trial treatment is discontinued, the subject remains in the trial and, given his agreement, will undergo the procedures for early treatment discontinuation and follow up as outlined in the [Flow Chart](#) and Section [6.2.3](#).

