### 6.2.3 Follow-up period and trial completion

For AE assessment, laboratory tests, recording of ECG and vital signs, and physical examination during the follow-up period, see Sections [5.2.2](#) to [5.2.5](#).

Subjects who discontinue treatment before the end of the planned treatment period should undergo the end-of-trial (EoT) Visit.

All abnormal values (including laboratory parameters) that are assessed as clinically relevant by the investigator will be monitored using the appropriate tests until a return to a medically acceptable level is achieved. (S)AEs persisting after a subject's EoT Visit must be followed until they have resolved, have been sufficiently characterised, or no further information can be obtained.

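### On the visible text, a dosed subject who leaves before 72 h has no scheduled post-dose C-SSRS, and the SAP table can be read as counting him with the all-No subjects

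*Protocol*

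**What the plan says.** Protocol 3.3.4 governs what happens at discontinuation: "At the time of discontinuation, a complete end of trial (EoT) examination will be performed, if possible". If this falls before the end of the residual effect period (REP, 36 h), the subject should also, where possible, "be questioned for AEs and concomitant therapies at or after the end of the REP". Section 6.2.3 repeats the main rule: "Subjects who discontinue treatment before the end of the planned treatment period should undergo the end-of-trial (EoT) Visit".

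The content of that visit is in footnote 4 of the SRD flow chart: "EoT examination includes physical examination, body weight, vital signs, ECG, safety laboratory, recording of AEs, and concomitant therapies". The BA/FE flow chart has the same list. A further footnote on the AE entry of the EoT row adds a conditional element: "Dissociative symptoms are reported as AEs and should be quantified with CADSS".

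Criterion 5 of Section 3.3.4.1 gives, among its examples of events that may lead to discontinuation, "unexplained hepatic enzyme elevations at any time during the trial, or development of suicidal ideation". The same section keeps the subject in the study: "Even if the trial treatment is discontinued, the subject remains in the trial and, given his agreement", follows the procedures in the flow chart and Section 6.2.3.

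On the analysis side, SAP 7.8.5.3 tabulates subjects by any C-SSRS question answered Yes and puts the alternative, all No or missing, in one parenthesis. SAP Section 7 sets the general rule for frequency tables: a missing category appears whenever values are missing, and percentages use all subjects in the set.

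**The concern.** The EoT list suits a completer, who had his C-SSRS and CADSS at the 72 h discharge assessment. Reused as the exit examination for someone who leaves sooner, it omits the trial's own suicidality instrument. Such a subject could leave because of suicidal ideation without a structured record of it.

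At stake are the completeness of one safety assessment in a first-in-human CNS trial and the accuracy of one table. If an unassessed subject sits in the same row as those who answered No to everything, the table reports reassurance that was never obtained. The primary endpoints are not materially affected.

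**Working it through.** No figure in the plan needs reproducing. The check is a reading of the flow charts followed by simple counts.

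**1. Where discontinuation leads.** Section 3.3.4 leads to the EoT examination. Section 3.3.4.1 points to the flow chart and Section 6.2.3, and Section 6.2.3 leads to the EoT visit. All routes end at footnote 4.

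**2. What the EoT row contains.** In both flow charts the row marks safety laboratory, physical/neurological examination, 12-lead ECG, vital signs and AE questioning. The C-SSRS and CADSS cells are blank. CADSS enters only through the AE footnote, when dissociative symptoms are reported.

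**3. Scheduled post-dose assessments, SRD part.** C-SSRS is marked at 72 h only (1 assessment); its other mark is at screening. CADSS is marked at 1, 2, 4, 24, 48 and 72 h (6 assessments). By time of exit:

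| Exit after dosing | C-SSRS obtained | CADSS obtained |
|---|---|---|
| 4 to <24 h | 0 of 1 | 3 of 6 |
| 24 to <48 h | 0 of 1 | 4 of 6 |
| 48 to <72 h | 0 of 1 | 5 of 6 |
| after the 72 h assessments | 1 of 1 | 6 of 6 |

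In the BA/FE part the single post-dose C-SSRS is at 72 h of each period. A subject who leaves in period 2 or 3 keeps those of earlier periods, so the gap concerns that dose only.

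**4. Size of one case.** SRD dose group: 1/6 = 16.7% of active subjects. BA/FE part: 1/12 = 8.3%.

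**5. Effect on the C-SSRS table.** Suppose, for illustration, that one of six active subjects leaves before 72 h and the other five answer No throughout. With missing pooled into No, the row shows (5 + 1)/6 = 100%. Under the rule in SAP Section 7 it shows 5/6 = 83.3% all No and 1/6 = 16.7% missing.

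**The case against.** The strongest objection is that the governing text is not visible. The table of contents lists Section 5.2.6.2 on suicidality assessment and Appendix 10.3.2 with the since-last-visit form of the C-SSRS, and SAP 7.8.5.3 defers to Section 5.2.6. None of that text is in the documents reviewed, and it may already require an event-triggered or exit C-SSRS. This stands: the point is something to confirm, not a proven omission.

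The second objection is that almost nobody is affected. Sections 1.4.7, 4.1.4 and 6.2.2 keep subjects on site for at least 72 h, and Section 1.4.7 requires a formal fitness assessment before discharge. An SRD subject has no further dose to discontinue. A BA/FE subject who stops between periods, after discharge, has already had that period's C-SSRS. What remains is mainly the subject who insists on leaving, and he cannot be compelled. This also stands and sets the size of the point. It does not remove it, because a departing subject can still be offered a questionnaire.

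Third, other safeguards exist: AE follow-up, the neurological examination at EoT, and assessment whenever the investigator sees a need (Section 5.2.7.2.1). They reduce the risk but do not schedule the instrument. The SAP wording can also be read as three outcomes, and individual results are listed; an explicit row would settle the reading.

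A reader might infer more than the documents support:

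- **That discontinuation cancels the remaining assessments.** Section 3.3.4.1 keeps the subject in the trial, so nothing is lost for one who stays.
- **That an exit EEG is needed.** SRD EEGs at 0:45, 1:15, 3 and 8 h give four recordings to anyone who leaves after 8 h, and an exit EEG would be an extra procedure.
- **That the dog convulsions make the gap urgent.** Section 1.2.3.2 places the generalised convulsions starting at about 24 h, in the dose range finding study, at 15 mg/kg. At 5 mg/kg there was a single episode at 28 h. The exposure margin for 5 mg/kg therefore cannot be attached to the 24 h events.
- **That escalation could pass over an early exit because two severe events are needed.** Section 1.4.7 also stops for drug-related, clinically relevant neurological changes indicating dose-limiting intolerance in a single subject. Section 3.1 permits escalation only if neither the Principal Investigator nor the Clinical Trial Leader has a safety concern.

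**Conclusion.** The point holds in a narrow form. On the visible text, a dosed subject who leaves before 72 h has 0 of 1 scheduled post-dose C-SSRS for that dose, although suicidal ideation is a listed reason to discontinue. SAP 7.8.5.3 can be read as counting him with the all-No subjects, contrary to SAP Section 7. The effect is at most one questionnaire per early leaver, and the documents give no basis for estimating how many there will be.

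The conclusion assumes that Section 5.2.6 does not already provide for the case and that the EoT rows of the flow charts were read correctly from the extracted tables. It is a minor safety and reporting improvement.

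**What to change.** First check Section 5.2.6. Unless it already covers the case, add one footnote to the EoT row of each flow chart: a dosed subject who leaves before 72 h is offered the C-SSRS and CADSS together with the EoT examination, given his agreement. If it does, a cross-reference from Section 3.3.4 is enough.

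In the SAP 7.8.5.3 table, show subjects with no post-dose assessment in their own row, apart from those who answered No throughout.

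The cost is one footnote per flow chart, one table row and a few minutes of questionnaires for a departing subject. Both instruments are already in use in the trial.

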#### 3.3.4.1 Discontinuation of trial treatment

An individual subject will discontinue trial treatment if:

1. The subject wants to discontinue trial treatment, without the need to justify the decision
2. The subject has repeatedly shown to be non-compliant with important trial procedures and, in the opinion of both, the investigator and sponsor representative, is not willing or able to adhere to the trial requirements in the future
3. The subject needs to take concomitant medication that interferes with the investigational medicinal product or other trial treatment
4. The subject can no longer receive trial treatment for medical reasons (such as surgery, adverse events (AEs), or diseases)
5. An AE or clinically significant laboratory change or abnormality occurs that the investigator assesses as warranting discontinuation of treatment. This may include cases of sustained symptomatic hypotension (BP <90/50 mmHg) or hypertension (BP

- >180/100 mmHg), clinically relevant changes in ECG requiring intervention, unexplained hepatic enzyme elevations at any time during the trial, or development of suicidal ideation
6. The subject has an elevation of AST and/or ALT  $\geq 3$ -fold ULN and an elevation of total bilirubin  $\geq 2$ -fold ULN (measured in the same blood sample) and/or needs to be followed up according to the DILI checklist provided in the ISF

In addition to these criteria, the investigator may discontinue subjects at any time based on his or her clinical judgment.

Even if the trial treatment is discontinued, the subject remains in the trial and, given his agreement, will undergo the procedures for early treatment discontinuation and follow up as outlined in the [Flow Chart](#) and Section [6.2.3](#).

#### 3.3.4.2 Withdrawal of consent to trial participation

Subjects may withdraw their consent to trial participation at any time without the need to justify the decision. If a subject wants to withdraw consent, the investigator should be involved in the discussion with the subject and explain the difference between trial treatment discontinuation and withdrawal of consent to trial participation, as well as explain the options for continued follow up after trial treatment discontinuation. See also Section [3.3.4.1](#) above.

#### 3.3.4.3 Discontinuation of the trial by the sponsor

Boehringer Ingelheim reserves the right to discontinue the trial at any time for any of the following reasons:

1. Failure to meet expected enrolment goals overall or at a particular trial site
2. New toxicological findings, serious adverse events, or any safety information invalidating the earlier positive benefit-risk assessment.
3. Violation of GCP, or the CTP impairing the appropriate conduct of the trial.
4. The sponsor decides to discontinue the further development of the investigational product.

The investigator/ trial site will be reimbursed for reasonable expenses incurred in case of trial termination (except if item 3 applies).

### 3.3.5 Replacement of subjects

#### SRD & BA/ FE-Part

A maximum of 4 subjects can replace those who dropped-out during the course the trial for safety reasons related or not related to the study medication. A replacement subject will be assigned a unique study subject number, and will be assigned to the same treatment as the subject he replaces.

## 4. TREATMENTS

### 4.1 INVESTIGATIONAL TREATMENTS

The investigational products have been manufactured by BI Pharma GmbH & Co. KG.

See also Section [1.2.7](#) and current IB [[c29289852](#)].

#### 4.1.1 Identity of the Investigational Medicinal Products

##### SRD-Part

The characteristics of the test product are given below:

|                             |  |
|-----------------------------|--|
| Substance:                  | BI 1569912   |
| Pharmaceutical formulation: | Powder for oral solution   |
| Source:                     | BI Pharma GmbH & Co. KG, Germany   |
| Unit strength:              | 0.625 mg/ mL; 0.25 mg, 0.75 mg, 2 mg, 5 mg, 10 mg, 20 mg, 30 mg, 40 mg, 50 mg QD |
| Posology:                   | 1-0-0  |
| Route of administration:    | Oral   |
| Duration of use:            | Single dose  |

The characteristics of the reference product (placebo) are given below:

|                             |                                  |
|-----------------------------|----------------------------------|
| Substance:                  | Not applicable, solvent only     |
| Pharmaceutical formulation: | Solvent only                     |
| Source:                     | BI Pharma GmbH & Co. KG, Germany |
| Unit strength:              | N/A                              |
| Posology:                   | 1-0-0                            |
| Route of administration:    | Oral                             |
| Duration of use:            | Single dose                      |

The matching placebo is the solvent for oral solution only (Tartaric acid 5 mg/mL)

##### BA/ FE-Part

Only the highest dose strength, reduced by a factor of at least 2, will be tested, as demonstrated in the SRD-Part to be safe and tolerable (refer also to Section [1.3.3](#) and Section [1.4.7](#)).

The characteristics of the test product are given below:

Substance: BI 1569912  
Pharmaceutical formulation: Tablet  
Source: BI Pharma GmbH & Co. KG, Germany  
Unit strength: 5 mg  
Posology: 1-0-0  
Route of administration: Oral  
Duration of use: Single dose in each treatment period

The characteristics of the test product are given below:

Substance: BI 1569912  
Pharmaceutical formulation: Tablet  
Source: BI Pharma GmbH & Co. KG, Germany  
Unit strength: 2.5 mg  
Posology: 1-0-0  
Route of administration: Oral  
Duration of use: Single dose in each treatment period

The characteristics of the test product are given below:

Substance: BI 1569912  
Pharmaceutical formulation: Tablet  
Source: BI Pharma GmbH & Co. KG, Germany  
Unit strength: 0.5 mg  
Posology: 1-0-0  
Route of administration: Oral  
Duration of use: Single dose in each treatment period

